**FORM: Application for Human Research**

| NUMBER | FORM DATE | PAGE |
|--------|-----------|----------|
| F200 | 02/2014 | 31 of 44 |

1039 and gender. Randomization will consist of permuted blocks to achieve balance over time. Repeated
1040 measures analysis of variance (ANOVA) and linear mixed-model approaches will be used for the primary
1041 analyses examining the efficacy of light treatment condition on measures of mood and sleep. Between
1042 group factors will correspond to the two light conditions (BL vs PL) and will control for any baseline
1043 differences in demographic variables and severity scores as appropriate. Based on specific hypotheses,
1044 separate ANOVAs will be performed for each type of dependent variable (e.g., subjective sleep scores,
1045 CAPS-2 symptom scores, mood scores, MRS metabolites). The relationship between these change
1046 indices and sleep variables will be analyzed using correlation and linear regression models in SPSS. Tests
1047 for normality will be conducted for all variables. In the case on non-normality, appropriate data
1048 transformation or non-parametric techniques will be employed (e.g., Kruskal-Wallis or Friedman tests for
1049 ANOVA; Mann-Whitney U or Wilcoxon for 2-group comparisons). Inflation of Type I error will be
1050 controlled first through the use of planned comparisons based on the hypotheses and the use of protected
1051 omnibus F-tests. Post-hoc analyses will be undertaken with protected comparisons (e.g., Tukey) or
1052 Bonferroni adjustment. Functional MRI data will be analyzed using statistical parametric mapping
1053 (SPM8) software, implementing the general linear model to compare pre- to post-therapy changes in
1054 functional responses between the active and placebo groups and across diagnostic groups, and sleep
1055 variables will be tested as covariates in the models. Finally, proton spectroscopy data for each of the
1056 metabolites will be quantified and compared for pre- to post-therapy changes in metabolite concentrations
1057 between the active and placebo treatment groups and across diagnostic groups. Type I error during
1058 neuroimaging will be controlled via whole brain False Discovery Rate (FDR) correction or small volume
1059 corrections using Family Wise Error (FWE) rate within *a priori* specified regions of interest. To handle
1060 missing data, we will first determine the potential cause of the data loss. Statistically, missing data can be

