1061 considered as falling into three types: 1) missing completely at random, 2) missing at random, or 3)
1062 missing not at random. The type of missing data will dictate the approach. Assuming type 1, and that the
1063 number of missing values is low, we will use a standard listwise deletion procedure. However, assuming
1064 that a larger number of values is missing, and data are not missing completely at random, we will be able
1065 to apply missing data imputation methods.

1066 **Power Analysis:** A power analysis based on a proposed sample size of 90 subjects suggested that
1067 with an omnibus 2 between-groups (BL vs. PL) x 2 within-subjects (pre- vs post-treatment) mixed design,
1068 assuming a moderate effect size ($f = .25$), and $\alpha = .05$, there should provide be adequate power to detect
1069 most effects. First, the primary hypotheses of the study focus on interaction effects across groups (i.e.,
1070 treatment x session interactions), which will have exceptional power ($1-\beta = 0.99$) to detect a moderate
1071 effect size at $\alpha = .05$ (see Figure 18A). Paired comparisons within each group of will also have excellent
1072 power of .91 to detect moderate effect size changes ($d = .50$), with 2-tailed tests (see Figure 18B).
1073 Without regard to group differences, a sample size of 90 would yield power = 0.84 to detect a moderate
1074 linear association (i.e., $r \geq .30$) between a predictor variable (e.g., average sleep; change in sleep
1075 parameters, PTSD symptom severity; neurocognitive performance; etc.) and an outcome variable (e.g.,
1076 fMRI signal intensity changes; spectroscopic metabolite changes; etc.), with a two-tailed test at $\alpha = .05$
1077 (see Figure 16). Thus, the proposed sample size of $n = 45$ per group appears to provide adequate power
1078 for testing the major hypotheses of the proposed study.

FORM: Application for Human Research

| NUMBER | FORM DATE | PAGE |
|---------------|------------------|-------------|
| F200 | 02/2014 | 32 of 44 |

1079 **Functional Image Pre-Processing:** Functional neuroimaging data will be preprocessed in SPM8
1080 [123]. Following standard algorithms, functional images will be slice-time corrected, co-registered to
1081 their anatomical T1-weighted images, realigned, unwarped to correct for field inhomogeneity, normalized
1082 to the standard three-dimensional space of the Montreal Neurological Institute (MNI), spatially smoothed

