**FORM: Application for Human Research**

| NUMBER | FORM DATE | PAGE |
|--------|-----------|----------|
| F200 | 02/2014 | 33 of 44 |

1120 subgenual and rostral ACC, VMPFC, and amygdala. Data will be analyzed at an FDR corrected
1121 significance level of $p < 0.05$.

1122 **MRS Analyses:** The goal will be to determine whether BL treatment is more effective than PL at
1123 altering brain metabolites that are associated with alertness, cognitive processing, and inhibitory capacity.
1124 All MRS processing will be carried-out in a fully automated fashion using methods previously published
1125 by our group [127]. Metabolite ratios will be derived as a ratio of each raw metabolite integral to the total
1126 sum of the creatine and phosphocreatine integrals, and will be T1-corrected using values previously
1127 reported in the literature. Our primary endpoints of interest are Glu (excitatory neurotransmitter), GABA
1128 (inhibitory neurotransmitter), and NAA (marker of neuronal energy production). Standard linear and
1129 mixed model approaches will be employed for comparing metabolite ratios between the active BL and
1130 placebo light conditions within the dorsal ACC and amygdala-hippocampal complex. As described
1131 above, all analyses will be undertaken with $\alpha = .05$, employing corrections for multiple comparisons (e.g.,
1132 Tukey post-hoc corrections; Bonferroni corrections) as appropriate. We expect that the active BL
1133 condition will lead to increased levels of GABA, N-acetyl-aspartate (NAA), and choline (Cho), and
1134 reduced glutamate and phosphocreatine (Cr) in the amygdala-hippocampal complex and anterior cingulate
1135 gyrus compared to the PL condition. Furthermore, it is expected that these changes will be linearly
1136 related to changes in sleep parameters and cognitive/symptom score changes from pre- to post-
1137 assessment.

1138 8) Risks to subjects

1139 Participation in this study may involve some risks or discomforts, which are described below.
1140

1141 During the study visits, subjects may be asked some questions during the brief clinical interview
1142 and on the questionnaires that deal with personal or emotional matters. These questions might cause
1143 psychological discomfort. Subjects may refuse to answer any questions that make them uncomfortable. If
1144 they reveal during these sessions that they are currently or have recently had thoughts of self-harm or

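### The 0.84 power for sleep–brain correlations is for one uncorrected test at alpha .05; it does not cover the corrected fMRI tests, and covers the metabolite tests only if they are left uncorrected

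*Combined protocol and SAP*

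**What the plan says.** The Power Analysis paragraph in Section 3, D. Data Analysis, makes a pooled claim across both arms: "Without regard to group differences, a sample size of 90 would yield power = 0.84 to detect a moderate" "linear association (i.e., $r \geq .30$) between a predictor variable" and an outcome. The example outcomes are "fMRI signal intensity changes; spectroscopic metabolite changes; etc.), with a two-tailed test at" alpha .05. The paragraph mentions no multiplicity adjustment, and it closes by calling 45 per group adequate for the major hypotheses.

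Other parts of the same section describe how these outcomes will be tested:

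- **fMRI, Global Statistical Analysis Approach.** Sleep variables enter the SPM models as covariates. Type I error in "neuroimaging will be controlled via whole brain False Discovery Rate (FDR) correction or small volume" corrections by FWE within pre-specified regions.
- **fMRI, ROI and Whole Brain Exploratory Analyses.** Region analyses use a small-volume FDR threshold of .05. Whole-brain analyses, labelled exploratory, use FWE at .05.
- **Correlations, Global Statistical Analysis Approach.** The relation of change indices to sleep variables is analysed by correlation and linear regression in SPSS. MRS metabolites are among the listed dependent variables. That sentence names no correction.
- **MRS Analyses.** All analyses are at alpha .05, "employing corrections for multiple comparisons (e.g"., Tukey or Bonferroni) where appropriate, with no divisor. On the outcomes: "Our primary endpoints of interest are Glu (excitatory neurotransmitter), GABA" and NAA, in two regions. The same paragraph expects metabolite changes to be linearly related to sleep changes.

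**The concern.** The power statement names two imaging outcomes and gives a figure that belongs to a single test with no correction. The plan corrects its fMRI analyses and may correct its MRS analyses, and it reports no power at any corrected threshold.

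Hypothesis 4 depends on these associations. Its heading expects sleep improvement to track brain changes, and 4b expects it to track neurochemistry. Aims 3 and 4 also present the correlational data as valuable even if the light has no effect, so these results would carry weight if Aim 1 fails. A reader told 0.84 expects a true r of .30 to be missed 16% of the time (1 − 0.84). That reader could take a null sleep–BOLD or sleep–metabolite result as evidence against a moderate link. At a corrected threshold the chance of missing it is higher.

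**Working it through.** **Inputs from the documents.** n = 90, r = .30, two-sided alpha = .05, stated power 0.84 (Power Analysis). Three primary metabolites in two regions (MRS Analyses).

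**Reproducing 0.84.**

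- Fisher z: power = Φ(atanh(r)·√(n − 3) − z). Here atanh(.30) = 0.3095 and √87 = 9.327, with product 2.887. Then Φ(2.887 − 1.960) = Φ(0.927) = 0.823.
- Noncentral t with 88 degrees of freedom: noncentrality √(n·r²/(1 − r²)) = √(90 × .09/.91) = 2.98, which gives 0.839.
- Simulation of bivariate normal data, 100,000 replicates: 0.826.

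The stated figure therefore reproduces as one two-sided test at .05 with no correction. One-sided versions give 0.89 to 0.91 and do not match.

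**Metabolite correlations, if Bonferroni were applied.** Replace alpha by .05/m, where m is the number of tests. The plan does not state m, so each row is conditional.

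| m | alpha | Fisher z | Noncentral t | Simulation |
|---|---|---|---|---|
| 1 | .05 | 0.823 | 0.839 | 0.826 |
| 2 | .025 | 0.741 | 0.758 | 0.744 |
| 3 | .0167 | 0.689 | 0.706 | 0.692 |
| 6 | .0083 | 0.598 | 0.613 | 0.599 |
| 10 | .005 | 0.532 | 0.544 | 0.532 |

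The row m = 3 would be the primary metabolites in one region. The row m = 6 assumes 3 primary metabolites × 2 regions against one sleep variable. The row m = 10 assumes the 5 metabolites with a stated expected direction × 2 regions.

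**Correlation needed for 0.84 power at m = 6.** r = tanh((2.638 + 0.994)/9.327) = tanh(0.389), or about .37.

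**FDR on a small set of outcomes.** For comparison, Benjamini–Hochberg was simulated with outcomes that share one sleep variable and are otherwise independent. Over 3 outcomes, power for a real r = .30 is 0.70 if one association is real and 0.81 if all three are. Over 6 outcomes it is 0.62 if one is real, 0.72 if three are and 0.80 if all six are. FDR power depends on how many associations are real. This simulation is not a model of the planned voxelwise analysis.

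**fMRI.** The effective per-voxel threshold cannot be read from the plan. FDR thresholds depend on the data, and the number of effective tests is not given. The general section names small-volume FWE where the ROI section names small-volume FDR. The documents therefore show that 0.84 is not the power of the planned test, but they do not supply another figure.

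**The case against.** The strongest reply is that the sum is right and openly labelled two-tailed at alpha .05, and that the Global Statistical Analysis Approach does contain the test it describes: correlation or regression in SPSS, with MRS metabolites among the outcomes and no correction named. That section controls Type I error first through planned comparisons and omnibus tests, and reserves Tukey and Bonferroni for post-hoc work. Hypothesis 4b is pre-specified. The MRS section's corrections apply only where appropriate, and follow a sentence about comparing the light conditions.

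For metabolites this reply largely stands. A reader might infer that Bonferroni is the planned method, since Tukey compares group means and does not fit a correlation, and so conclude that power is about 0.60 or lower. The documents do not support that step. No family is defined for the sleep correlations, the six-test set is a construction, and smaller Bonferroni families or FDR mostly give higher values. What remains is that the two sections leave open whether these tests are corrected.

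For fMRI the reply does not help. The SPSS sentence does not list fMRI signal among its examples, and extracting one mean per region is not described. Sleep enters the SPM models, where correction is specified. A reader might put in a per-voxel alpha such as .001, which gives 0.34 to 0.35, but that threshold is an assumption. Power at one voxel is also not the power to find an association somewhere in a region, and the whole-brain FWE analyses are declared exploratory.

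It is also fair that the paragraph identifies the primary hypotheses with treatment-by-session interactions. The sample size does not rest on the correlations.

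**Conclusion.** The concern holds in a limited form. The 0.84 is correct for one unadjusted two-sided correlation of .30 with 90 participants, so this is not an arithmetic error. The fault is that the figure is attached to outcomes tested differently.

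- **fMRI:** 0.84 does not apply, because the planned tests are corrected. No single replacement figure can be derived.
- **MRS:** 0.84 applies only to a single correlation left uncorrected, and the plan does not say whether that is intended. Under Bonferroni, power would be below 0.80 from two tests on, ranging from 0.74–0.76 at 2 tests to 0.53–0.54 at 10. With the assumed family of six, a true r of .30 would be missed about 40% of the time (1 − 0.60), against the 16% implied.

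The MRS sizes rest on an assumed Bonferroni correction and assumed family sizes, with all 90 participants contributing data.

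**What to change.** In the Power Analysis paragraph:

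1. Limit the 0.84 to a single, pre-named, unadjusted correlation.
2. Remove fMRI signal change from the examples, or state that corrected voxelwise sleep–BOLD associations are not covered by that figure.
3. For the sleep–metabolite correlations, state whether they are corrected and over which family, and give the power at that threshold. Until the family is chosen, the range for 2, 3, 6 and 10 tests can be shown as conditional. If six is chosen with Bonferroni, add that 0.84 power needs r of about .37.
4. Qualify the closing claim of adequate power, so that a null imaging result under Hypothesis 4 is not read as excluding a moderate association.

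The MRS Analyses and Global Statistical Analysis Approach paragraphs should give the same answer on item 3. The choice of family belongs to the investigators. The cost is wording, and a less favourable stated power if correction is chosen. Enrolment and procedures do not change.

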**FORM: Application for Human Research**

| NUMBER | FORM DATE | PAGE |
|--------|-----------|----------|
| F200 | 02/2014 | 33 of 44 |

1120 subgenual and rostral ACC, VMPFC, and amygdala. Data will be analyzed at an FDR corrected
1121 significance level of $p < 0.05$.

1122 **MRS Analyses:** The goal will be to determine whether BL treatment is more effective than PL at
1123 altering brain metabolites that are associated with alertness, cognitive processing, and inhibitory capacity.
1124 All MRS processing will be carried-out in a fully automated fashion using methods previously published
1125 by our group [127]. Metabolite ratios will be derived as a ratio of each raw metabolite integral to the total
1126 sum of the creatine and phosphocreatine integrals, and will be T1-corrected using values previously
1127 reported in the literature. Our primary endpoints of interest are Glu (excitatory neurotransmitter), GABA
1128 (inhibitory neurotransmitter), and NAA (marker of neuronal energy production). Standard linear and
1129 mixed model approaches will be employed for comparing metabolite ratios between the active BL and
1130 placebo light conditions within the dorsal ACC and amygdala-hippocampal complex. As described
1131 above, all analyses will be undertaken with $\alpha = .05$, employing corrections for multiple comparisons (e.g.,
1132 Tukey post-hoc corrections; Bonferroni corrections) as appropriate. We expect that the active BL
1133 condition will lead to increased levels of GABA, N-acetyl-aspartate (NAA), and choline (Cho), and
1134 reduced glutamate and phosphocreatine (Cr) in the amygdala-hippocampal complex and anterior cingulate
1135 gyrus compared to the PL condition. Furthermore, it is expected that these changes will be linearly
1136 related to changes in sleep parameters and cognitive/symptom score changes from pre- to post-
1137 assessment.

1138 8) Risks to subjects

1139 Participation in this study may involve some risks or discomforts, which are described below.
1140

1141 During the study visits, subjects may be asked some questions during the brief clinical interview
1142 and on the questionnaires that deal with personal or emotional matters. These questions might cause
1143 psychological discomfort. Subjects may refuse to answer any questions that make them uncomfortable. If
1144 they reveal during these sessions that they are currently or have recently had thoughts of self-harm or
1145 suicide, appropriate follow-up evaluation and referral for care will be ensured. Results of the clinical
1146 evaluation will be kept in a locked cabinet and identified using only subject unique study identification
1147 number.

1148 Subjects may find the sensation of the electric shock used in the picture-viewing task to be
1149 uncomfortable. However, they will be able to choose their own level of shock, which should be strong
1150 enough to annoying or uncomfortable, but not painful. The apparatus that provides the shock is powered
1151 by a 9-volt electric battery, identical to those used in toy electronics. These mild shocks are not dangerous
1152 or harmful, but may be annoying.

1153 Unlike X-rays or CAT scans, magnetic resonance (MR) technology does not use ionizing
1154 radiation. Instead, it uses strong magnetic fields and radio waves to collect the images and data. With the
1155 exception of one sequence (MEGA-PRESS spectroscopy work-in-progress (WIP) pulse sequence), all
1156 MRI procedures involved are standard. The radio frequency exposure, magnetic fields and gradients, and
1157 noise levels produced by the MRI sequences used in this study are no greater than or fall below the FDA's
1158 limits, so subjects are exposed to no greater risk than those of routine MRI scans (see *MEGA-PRESS*
1159 *Sequence Manual.pdf* and *Request allowance for running MEGA-PRESS WIP* ([name], [name], et al,

**FORM: Application for Human Research**

| NUMBER | FORM DATE | PAGE |
|--------|-----------|----------|
| F200 | 02/2014 | 34 of 44 |

1160 2019). During the scan, subjects will wear a birdcage coil around their heads; this is an FDA-cleared
1161 device and its use in this study will be as approved by FDA.

1162
1163 The four risks the FDA associates with MRI scanning are: 1) tissue heating due to RF fields, 2)
1164 peripheral nerve stimulation due to quick changes in magnetic field, 3) hearing damage due to acoustic
1165 noise, and 4) force and torque on magnetic materials in or on a participant. That said, the FDA lists "MRI
1166 Devices within FDA specified parameters" as non-significant risk devices. The research scanner in the
1167 TBIR fits within this description. With regard to tissue heating and peripheral nerve stimulation, the
1168 Siemens scanner is not capable of running a sequence that is outside the FDA safety guidelines. With
1169 regard to hearing damage, volunteers wear ear protection when in the scanner. In addition, any non-FDA
1170 approved sequence conducted is within FDA parameters for tissue heating, peripheral nerve stimulation,
1171 and hearing damage.

1172
1173 With regard to force and torque on magnetic materials, anyone entering the magnet room must remove
1174 all metal objects from their body. In addition, significant risks may exist for people with:

1175
1176 • Cardiac pacemakers
1177 • Metal clips on blood vessels (also called stents)
1178 • Artificial heart valves
1179 • Artificial arms, hands, legs, etc.
1180 • Brain stimulator devices
1181 • Implanted drug pumps
1182 • Ear implants
1183 • Eye implants or known metal fragments in eyes
1184 • Exposure to shrapnel or metal filings (wounded in military combat, sheet metal workers, welders, and
1185 others)
1186 • Other metallic surgical hardware in vital areas
1187 • Certain tattoos with metallic ink
1188 • Certain transdermal (skin) patches such as NicoDerm (nicotine for tobacco dependence), Transderm
1189 Scop (scopolamine for motion sickness), or Ortho Evra (birth control)

1190
1191 Volunteers are screened before entering the magnet to be sure they do not have any of these items. If
1192 subjects are unsure whether they have any of these items in their body, they will be informed that most
1193 would have been implanted as part of a surgical procedure, and that trying to remember past operations
1194 may help them remember if they have any implanted devices or history of exposure to shrapnel or metal
1195 filings, and, if so, they will not be able to participate in this study.

1196
1197 Significant risks also can arise if certain materials (many types of metal objects) are brought into the
1198 scanning area, as they can be pulled into the magnet at great speed, which might cause serious injury.
1199 Therefore, these types of items are not permitted in the scanning area. Subjects will not be allowed to
1200 bring anything with them into the scanning room.

**FORM: Application for Human Research**

| NUMBER | FORM DATE | PAGE |
|--------|-----------|----------|
| F200 | 02/2014 | 35 of 44 |

1202 The MR exams are painless, and except for pulsating sounds or vibrations, subjects will not be aware that
1203 scanning is taking place.

1204
1205 The scans will take place on a 3T scanner, which are approved by the FDA for routine clinical studies in
1206 children and adults. However, as part of the MRI session, subjects will receive an MRI scan that measures
1207 chemicals in the brain, the MEGA-PRESS sequence, that is not FDA approved, though it does comply
1208 with the same FDA guidelines used for routine FDA approved MRI scans. Therefore, all MRI scans used
1209 in this study do not expose subjects to any more risk than a routine MRI exam.

1210
1211 Although there are no known risks from these scans, there could be adverse effects that are delayed or
1212 very mild, such that they have not yet been recognized. Most people experience no ill effects from these
1213 scans, but some people do report claustrophobia (fear of being in enclosed small spaces), dizziness, mild
1214 nausea, headaches, and a metallic taste in their mouth, double vision, or the sensation of flashing lights.
1215 Some subjects also experience feelings of panic and/or anxiety. These symptoms are rare, and if present,
1216 disappear shortly after leaving the scanner. **In addition to these physical risks, the MRI system can be**
1217 **psychologically unsettling to some volunteers that are bothered by loud noises or small spaces.**

1218
1219 Volunteers can ask to be removed from the scanner at any point during the procedure without any
1220 repercussions.

1221
1222 Steps taken to minimize risk:

1223
1224 For the first three MRI risks described above, all sequences operate within the FDA limits of non-
1225 significant risk. For the fourth risk, force/torque on magnetic materials, all volunteers are checked
1226 multiple times for these materials before entering the magnetic field. In addition, volunteers can ask to be
1227 removed from the scanner at any point during the procedure without any repercussions.

1228 Subjects will be screened for any contraindications to MRI and magnetic materials. The investigator or
1229 MRI Technologist will explain the MRI system and the scan that they are about to take part in. The
1230 volunteer will be asked to lie down on the scanner bed. Some part of the volunteer's body may be covered
1231 or enclosed within an FDA or UofA HSPP approved MRI coil. The volunteer may be asked to interact
1232 with a peripheral system such as a button, joystick, or TV system before, during, or after the scan.

1233
1234 Although both light devices (placebo [PL] and blue light [BLT]) are safe to use (Sliney, 2009,
1235 2006; Apollo Health, 2009), we will minimize unnecessary direct exposure to the bright lights to reduce
1236 the possibility of discomfort or persistent visual symptoms. Although looking directly at the LEDs for
1237 brief periods is not known to be harmful, it is unnecessary and may lead to glare, eyestrain, or other
1238 irritating visual sensations that can be easily avoided by keeping the panel at an angle in the peripheral
1239 vision. It is sufficient that the light reaches the eyes indirectly from the side. Looking directly at the LEDs
1240 does not provide any additional benefit. Prolonged staring at the LEDs could lead to significant eye
1241 irritation, lingering afterimages, or other symptoms such as headaches. Although the light emissions of
1242 the device are well within safe limits and no problems have ever been reported, we want to minimize any
1243 risks or discomforts. While extremely unlikely, it is possible that prolonged continuous staring at the

